### **Physical Examination**

A full physical examination will be performed at Screening, Week 12 and Week 56/Premature Discontinuation Visits and must include an assessment of extra-intestinal manifestations (EIMs) and a count of the number of cutaneous fistulas as in [Table 3](#). All other visits are symptom based but must include a count of the number of cutaneous fistulas. A count of the number of cutaneous fistulas draining upon gentle compression will be performed during each physical exam. Fistulas will be classified as abdominal or perianal/anal. Physical exam abnormalities noted by the investigator at Baseline (including fistulas and fissures) will be recorded in the subject's medical history.

Abnormalities noted after the Baseline visit will be evaluated and documented by the investigator as to whether they are AEs.

Additionally physical examination findings that are related to or part of each subject's medical history will be captured on the appropriate medical history eCRFs.

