### **Endoscopy**

An endoscopy will be performed on the following visits:

- During Screening\*
- Week 12
- Week 56/Premature Discontinuation if PD occurs after Week 26

It is expected all subjects will have a Week 12 and 56/PD Endoscopy. Site staff should schedule the Week 12 Endoscopy during the Baseline visit, if possible. For subjects that PD, the site should attempt to reschedule the Endoscopy prior to the discontinuation visit.

\*An endoscopy performed before the Screening visit, may be used as the Screening endoscopy, with the approval of the AbbVie Study Designated Physician, if the following conditions are met:

1. biopsy confirmation of the diagnosis is available according to section "Biopsy During Endoscopy" below.
2. the endoscopy took place within 45 days before Baseline Visit.
3. the endoscopy was performed and recorded in a video format as the endoscopic eligibility will be determined by the central reviewers. The same endoscopist, where possible, should perform all endoscopies.

All ileocolonoscopies should be performed and recorded in a video format during the Screening Period or endoscopy performed within 45 days before Baseline and the

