Table 4. Visit Windows for Analysis of Chemistry, Hematology, Urinalysis, hs-CRP, Fecal Calprotectin, Abdominal Pain Rating Scale, IBDQ, EQ-5D, and WPAI for Maintenance Study

Scheduled Week	Nominal Day	Time Window (Rx Day Range)
Week 12 (Week 0 of Maintenance Study)	1 ^a	≤ 1
Week 26 (Week 14 of Maintenance Study)	99	2 – 148
Week 40 (Week 28 of Maintenance Study)	197	149 – 253
Week 56 (Week 44 of Maintenance Study)	309	254 – 379

Rx Day = date of visit – date of first study drug injection in double-blind maintenance study + 1

- a. Day of first dose of study drug in double-blind maintenance study. If a subject has not taken any study drug during Maintenance Study, the randomization date will be use as Day 1 of Maintenance Study.

Table 5. Visit Windows for Analysis of SES-CD for Maintenance Study

Scheduled Week	Nominal Day	Time Window (Rx Day Range)
Week 12 (Week 0 of Maintenance Study)	1 ^a	≤ 1
Week 56 (Week 44 of Maintenance Study)	309	2 – 379

Rx Day = date of visit – date of first study drug injection in double-blind maintenance study + 1

- a. Day of first dose of study drug in double-blind maintenance study. If a subject has not taken any study drug during Maintenance Study, the randomization date will be use as Day 1 of Maintenance Study.

Table 6. Visit Windows for Analysis of Fistulas and EIM for Maintenance Study

Scheduled Week	Nominal Day	Time Window (Rx Day Range)
Week 12 (Week 0 of Maintenance Study)	1 ^a	≤ 1
Week 56 (Week 44 of Maintenance Study)	309	2 – 379

Rx Day = date of visit – date of first study drug injection in double-blind maintenance study + 1

- a. Day of first dose of study drug in double-blind maintenance study. If a subject has not taken any study drug during Maintenance Study, the randomization date will be use as Day 1 of Maintenance Study.

CD-Related Concomitant Corticosteroid Therapy

Subjects in whom the CD-related corticosteroids (systemic or rectal corticosteroids) that were not being taken at Induction Baseline and are initiated during the study or who have equivalent dose of these medications increased to greater than the dose taken at Induction Baseline will be censored for efficacy assessments (i.e., will be considered non-responders for categorical endpoints and will have last non-missing values carried forward for non-categorical assessments) from that point through the end of the study. These subjects will continue to be evaluated in the safety population.

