For safety related analyses, if multiple measurements are made for a particular laboratory or vital sign parameter on the same day for the same subjects, the later time one will be used if there is time or the average of the values will be used in the analyses of change from Baseline. For summaries and listings for shift from baseline and potentially significant values, all collected values within the pre-specified treatment window will be used.

Definition of Analysis Windows

Since subjects do not always adhere to the study visit schedule, the following rules will be applied to assign actual visits to protocol-specified visits including early termination visits. For each study visit mentioned in the protocol, a nominal or target day will be selected to represent the corresponding visit along with a window around the target day. Windows will be selected in a non-overlapping fashion so that a date collected on the CRF does not correspond to multiple visit windows. Moreover, windows will not discard any Post-Baseline measurement recorded on the CRF. If a subject had two or more actual visits in one visit window, the visit closest to the schedule visit will be used as the study visit for that window. If two visits are equidistant from the target, then the later visit will be used for reporting. If more than one assessment is collected on the same day, then the average of those assessments will be used in analyses.

Table 2. Visit Windows for Analysis of Efficacy Variables (Except IBDQ, EQ-5D, WPAI, and SES CD), hs-CRP, Urinalysis and Vital Signs for Induction Study

Scheduled Week	Nominal Day	Time Window (Rx Day Range)
Week 0	1 ^a	≤ 1
Week 2	15	2 – 22
Week 4	29	23 – 36
Week 6	43	37 – 50
Week 8	57	51 – 71
Week 12	85	72 – 98 ^b

Rx Day = date of visit – date of first study drug injection in double-blind induction study + 1

- a. Day of first dose of study drug in double-blind induction study. If a subject has not taken any study drug during Induction Study, the randomization date will be use as Day 1.
- b. Rx Day 98, or first dose of maintenance, or first dose of study drug in Study M14-347, whichever earlier.

Table 3. Visit Windows for Analysis of IBDQ, EQ-5D, and WPAI

Scheduled Week	Nominal Day	Time Window (Rx Day Range)
Week 0	1 ^a	≤ 1
Week 4	29	2 – 43
Week 8	57	44 – 71
Week 12	85	72 – 98 ^b

Rx Day = date of visit – date of first study drug injection in double-blind induction study + 1

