- a. Day of first dose of study drug in double-blind induction study. If a subject has not taken any study drug during Induction Study, the randomization date will be use as Day 1.
- b. Rx Day 98, or first dose of maintenance, or first dose of study drug in Study M14-347, whichever earlier.

Table 4. Visit Windows for Analysis of Chemistry and Hematology for Induction Study

Scheduled Week	Nominal Day	Time Window (Rx Day Range)
Week 0	1 ^a	≤ 1
Week 2	15	2 - 22
Week 4	29	23 – 43
Week 8	57	44 – 71
Week 12	85	72 – 98 ^b

Rx Day = date of visit – date of first study drug injection in double-blind induction study + 1

- a. Day of first dose of study drug in double-blind induction study. If a subject has not taken any study drug during Induction Study, the randomization date will be use as Day 1.
- b. Rx Day 98, or first dose of maintenance, or first dose of study drug in Study M14-347, whichever earlier.

Table 5. Visit Windows for Analysis of SES-CD, Fistulas, and EIM for Induction Study

Scheduled Week	Nominal Day	Time Window (Rx Day Range)
Week 0	1 ^a	≤ 1
Week 12	85	2 – 168 ^b

Rx Day = date of visit – date of first study drug injection in double-blind induction study + 1

- a. Day of first dose of study drug in double-blind induction study. If a subject has not taken any study drug during Induction Study, the randomization date will be use as Day 1.
- b. Rx Day 168, or first dose of maintenance + 7 days, or first dose of study drug in Study M14-347 + 7 days, whichever earlier. No + 7 days for Fistulas and EIM.

Table 6. Visit Windows for Analysis of Fecal Calprotectin for Induction Study

Scheduled Week	Nominal Day	Time Window (Rx Day Range)
Week 0	1 ^a	≤ 1
Week 4	29	2 – 57
Week 12	85	58 – 112 ^b

Rx Day = date of visit – date of first study drug injection in double-blind induction study + 1

- a. Day of first dose of study drug in double-blind induction study. If a subject has not taken any study drug during Induction Study, the randomization date will be use as Day 1.
- b. Rx Day 112, or first dose of maintenance, or first dose of study drug in Study M14-347, whichever earlier.

CD-Related Concomitant Corticosteroid Therapy

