Subjects in whom the CD-related corticosteroids (systemic or rectal corticosteroids) that were not being taken at Baseline and are initiated during the study or who have equivalent dose of these medications increased to greater than the dose taken at Baseline will be censored for efficacy assessments (i.e., will be considered non-responders for categorical endpoints and will have last non-missing values carried forward for non-categorical assessments) from that point through the end of the study. These subjects will continue to be evaluated in the safety population.

The equivalent steroid dose will be determined based on the table below:

Corticosteroid	Equivalent Dose (mg)
Cortisone	25
Hydrocortisone	20
Prednisone	5
Prednisolone	5
Triamcinolone	4.0
Methylprednisolone	4.0
Betamethasone	0.75
Dexamethasone	0.75
Budesonide	1
Beclomethasone	5
Beclometasone	5

Definition of Missing Data Imputation

The following imputation methods will be used to impute missing values in the efficacy analyses. In addition, an observed case analysis will be performed.

Non-Responder Imputation (NRI)

The NRI approach is used for binary efficacy variables. These variables can take values of 'Achieved' or 'Not Achieved' or may be missing for any reason including discontinuation from study. According to the NRI imputation approach, all missing values will be considered as 'Not Achieved.'

Last Observation Carried Forward (LOCF)

For all variables (categorical variables and continuous variables), the following rules will be used for the LOCF approach:

1. Baseline and Pre-Baseline values will not be used to impute the missing Post-Baseline values.

2. Missing values after Study Day 1 will be imputed using the latest non-missing values after Day 1 and prior to the missing value. If there are no non-missing values after Baseline, then the LOCF value will be missing.

Mixed-Effect Model Repeated Measure (MMRM)

The MMRM model will be used for continuous efficacy variables with longitudinal data as a sensitivity analysis. The MMRM model includes the baseline values as covariate; randomization strata, region (US versus non-US), treatment, time point and treatment-by-time point interaction as fixed effects; and subjects within treatment as random effect. An unstructured (co)variance structure will be used to model the within-subject error. The comparison at a time point will be the contrast between treatments at that time point.

Observed Case (OC)

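### The Week 12 and Week 56 windows for SES-CD and fistulas open on Day 2, so an early-discontinuation value can stand as the outcome in place of non-responder imputation

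*SAP*

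**What the plan says.** **Windows.** Induction SAP 6.0, Table 5, has a single post-Baseline window for SES-CD, fistulas and extra-intestinal manifestations (EIM). It is labelled Week 12, runs from Rx Day 2 to 168 and has nominal Day 85. Footnote b ends it at "Rx Day 168, or first dose of maintenance + 7 days, or first dose of study drug in Study M14-347 + 7 days, whichever earlier", and withholds the extra 7 days from fistulas and EIM. The footnote governs only the upper end; the Day 2 opening is in the table row. Maintenance SAP 6.0, Table 5 (SES-CD) and Table 6 ("Visit Windows for Analysis of Fistulas and EIM for Maintenance Study") likewise have one post-baseline window each. Both are labelled Week 56, run from Rx Day 2 to 379 counted from the first maintenance dose, and have nominal Day 309.

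**Assignment.** Under Definition of Analysis Windows in both SAPs, the rules are "applied to assign actual visits to protocol-specified visits including early termination visits". Windows are said not to overlap and to discard no post-Baseline measurement. With several visits in a window, "the visit closest to the schedule visit will be used as the study visit for that window".

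**Imputation.** Binary variables "may be missing for any reason including discontinuation from study". The rule is then: "According to the NRI imputation approach, all missing values will be considered as 'Not Achieved".

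**Collection.** Protocol 5.3.1.1, Physical Examination: "A count of the number of cutaneous fistulas draining upon gentle compression will be performed during each physical exam". Protocol 5.3.1.1, Endoscopy, lists a scan at "Week 56/Premature Discontinuation if PD occurs after Week 26".

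**The concern.** A value inside a window is not missing, so NRI has nothing to act on. Where the window opens on Day 2, almost any post-Baseline value from a subject who has left becomes the named Week 12 or Week 56 result. The CDAI windows are much narrower. The same dropout is therefore a failure on clinical remission and may be a success on endoscopic response or fistula closure.

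Fistulas are the clearest case: they are counted at every visit, so one post-Baseline examination is enough to avoid NRI. Week 56 endoscopy comes next, because a scan is scheduled for subjects who discontinue after Week 26. Results presented as durable response at Week 56 could then include subjects who stopped long before. If dropout differs between arms, the comparison shifts.

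**Working it through.** **1. Distance from the target day** (nominal day minus opening day)

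| Endpoint | Window (Rx Day) | Nominal | Earliest value |
|---|---|---|---|
| Week 12 SES-CD, fistulas | 2–168 | 85 | 85 − 2 = 83 days early |
| Week 12 CDAI | 72–98 | 85 | 85 − 72 = 13 days early |
| Week 56 SES-CD, fistulas | 2–379 | 309 | 309 − 2 = 307 days early |
| Week 56 CDAI | 282–379 | 309 | 309 − 282 = 27 days early |

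**2. Three subjects traced through the rules**

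- *Leaves after the Week 2 visit (Day 15), fistula not draining that day.* The count falls in 2–168 and is the only one, so Week 12 closure is achieved, 85 − 15 = 70 days early. CDAI falls in the Week 2 window (2–22); Week 12 CDAI is missing and becomes a non-response.
- *Leaves after the Week 14 visit (maintenance Rx Day 15), fistula not draining.* Week 56 closure is achieved, 309 − 15 = 294 days early. Week 56 CDAI is missing.
- *Discontinues just after Week 26 (about Rx Day 99) with the scheduled scan.* The scan is analysed as Week 56, 309 − 99 = 210 days, or 30 weeks, early. CDAI falls in the Week 26 window (79–106); Week 56 CDAI is missing.

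**3. Overlap.** The first maintenance dose is Rx Day 1, so 7 days later is Rx Day 8. A scan on maintenance Day 2 to 8 is inside the Induction Week 12 window and also inside the Maintenance Week 56 window, against the SAPs' own non-overlap rule. The Maintenance SAP's own Week 12 window ends at Rx Day 1, so the two SAPs place that scan at different visits. If Week 12 status comes from the induction analysis and there is no later scan, one endoscopy could be both the qualifying Week 12 response and the Week 56 success (Maintenance SAP 10.2, first endpoint).

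**4. Planned sensitivity analysis.** For endoscopy both SAPs rule out LOCF and rely on observed cases (OC). OC uses the same windowed value, so the early scan stays in and the effect is not visible.

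**5. Size for the endoscopic co-primary.** Inputs from Induction SAP 4.3: 66% against 44%, 300 against 200 subjects, Fisher's exact test, two-sided 0.05, power stated as about 99%. Exact enumeration gives 0.998, so the plan's figure is reproduced.

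The documents give no discontinuation or early-scan rate, so the rest is an assumed range. Let *d* be the share of an arm that stops early with an in-window scan, *q* the response rate on those scans, and *p* the planned response rate.

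- Rate under the present window: *p*(1 − *d*) + *qd*. Rate under NRI: *p*(1 − *d*). The excess in one arm is *qd*.
- Equal *d* in both arms, all counted as non-responders:

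| *d* | Higher | Standard | Exact power |
|---|---|---|---|
| 2% | 64.7% | 43.1% | 0.997 |
| 5% | 62.7% | 41.8% | 0.995 |
| 10% | 59.4% | 39.6% | 0.991 |
| 15% | 56.1% | 37.4% | 0.983 |

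- Unequal *d*, same *q* in both arms: the difference moves by *q*(*d*_higher − *d*_standard). For 5% against 10%: 0.20 × (−0.05) = −1.0 point and 0.44 × (−0.05) = −2.2 points. For 5% against 15%: 0.20 × (−0.10) = −2.0 and 0.44 × (−0.10) = −4.4 points. Exchanging the arms reverses the sign.

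For the Week 56 and fistula endpoints the excess is again *qd* per arm, but the documents give no value to anchor either term.

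**The case against.** The strongest reply is that the choice is deliberate and open. The SAPs say that early termination visits are windowed, and Induction SAP 12.2 explains that the SES-CD window was widened so that no induction endoscopy is lost. Discontinuation procedures are due within 2 weeks of the last dose (Protocol 5.4.1), so a scheduled discontinuation scan reflects recent treatment. The nearest-visit rule leaves subjects with a scan near the target day unaffected. Fistula endpoints are non-ranked subsets, and the Maintenance Study is exploratory with no sample-size calculation. All of this stands and limits the stakes. It does not explain a single window for a measure taken at every visit, a Week 56 window opening on Day 2, or the overlap. Section 12.2 also says the Week 12 window should reflect the 12-week induction treatment, which a scan in the first days does not.

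Three stronger readings are tempting, and the documents do not support them.

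- *NRI never applies.* It does when there is no in-window value, which covers early induction dropouts without a scan, and when more than 8 SES-CD variables are missing. Steroid-censored subjects are non-responders whatever the window. No discontinuation scan is listed before Week 26, although the protocol also asks sites to try to reschedule the endoscopy before a discontinuation visit, so some early scans may exist.
- *The SAP promises that discontinuation is failure.* It promises that missing values are failures; discontinuation is one reason for a value to be missing.
- *Calprotectin and IBDQ are equally affected.* Ranked endpoint 6 (calprotectin change) is continuous with LOCF as primary. Ranked endpoints 7 and 8 also need hs-CRP in Day 23–36. Among ranked endpoints the Week 4 IBDQ window (Day 2–43) reaches only number 13, which is minor.

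**Conclusion.** The point holds for SES-CD and fistulas at Week 12 and Week 56: an early value, where one exists and none is closer to the target day, replaces NRI. It is firmest for fistula closure and for Week 56 endoscopy, and the double placement of a maintenance Day 2 to 8 scan is a plain inconsistency between the two SAPs.

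The size cannot be fixed from the documents. Under the assumed unequal dropout the Week 12 endoscopic difference moves by about 1 to 4 points, in a direction that depends on which arm loses more subjects. Power for the endoscopic co-primary stays at about 0.98 or higher with up to 15% affected equally in both arms. A reader might infer that the co-primary result is at risk or biased in favour of one regimen; nothing in the documents shows that. The clinical co-primary is not touched, since Week 4 CDAI uses Day 23–36. The change should be made, but it is not critical to the trial's main conclusion.

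**What to change.** 1. **Fistulas.** Replace the single windows by the existing CDAI visit windows: Induction Table 2 (Week 12 = Day 72–98) and Maintenance Table 3 (Week 56 = Rx Day 282–379). The Maintenance CDAI windows run without a gap from Rx Day 2 to 379, so every maintenance count keeps a visit. This also settles a double listing, since the title of Induction Table 2, read literally, already covers fistulas.
2. **Week 56 SES-CD.** Open the window at Rx Day 282, as for CDAI. This removes the overlap with the Induction Week 12 window.
3. **Week 12 SES-CD.** Open the window at Day 72 and keep the existing upper limits, including first dose plus 7 days. At minimum, report this as a sensitivity analysis of the endoscopic co-primary.
4. **Handling.** State that values outside these windows are missing for the main analysis and go to NRI. Keep the present windows as a sensitivity analysis so that no scan is lost, and amend the sentence saying that windows discard no measurement.

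The cost is confined to the SAP window tables and one extra set of outputs; no data collection changes. Some early scans and counts leave the main analysis, and reported response rates may be slightly lower.

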### **Stool Samples Collected**

#### **Fecal Calprotectin**

Fecal calprotectin will be performed for all subjects as indicated in [Table 3](#). If subjects are unable to provide a sample at the site visit, subjects will be sent home with a stool sample supply kit and the site will give instructions to assist with collection procedures. The fecal calprotectin sample collected during the Screening Period will be used as the

baseline. All stool samples should be collected before any bowel preparation for endoscopy is started and returned to the site within 3 days of collection.

The fecal calprotectin results will remain blinded to Investigator, study site personnel and the subject throughout the study.

The central laboratory will be utilized to process and provide results for these laboratory tests.

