#### Clinically Adjusted (CA) Regimen:

Subjects randomized to the clinically adjusted regimen will receive 40 mg adalimumab every other week beginning at Week 12. The adalimumab dose will be escalated to every week starting as early as Week 14 if the subject's CDAI is  $\geq$  220 or hs-CRP  $\geq$  10 mg/L (using results from the prior or current visit). These subjects will also be allowed to escalate at unscheduled visits that may occur only on Weeks 16, 18, 22, 24, 30, 32, 36, 38, 44, 46, 50, 52 and 54. Once subjects in the CA regimen are escalated, they will remain on 40 mg ew dosing.

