**Study Drug Dosing Schedule**

Subject Number: \_\_\_\_\_

You will require subcutaneous injections throughout the study.

You will receive the following number of injections during the study:

- Baseline Visit (the first visit to receive study medication for this study), you will receive 4 injections (2 kits) at the clinic.
- Week 1 you will administer 4 injections (2 kits) at home.
- Week 2 you will receive 4 injections (2 kits) at the clinic.
- Week 3 you will administer 4 injections (2 kits) at home.
- At Weeks 4, 6, 8, 12, 14, 20, 26, 28, 34, 40, 42 and 48 you will receive 1 injection at the clinic.
- At Weeks 10, 13, 15 – 19, 21 – 25, 27, 29 – 33, 35 – 39, 41, 43 – 47, 49 – 55 you will administer 1 injection at home.

For all doses, kits must be used in the order dispensed. All doses of study medication must be taken in order, starting with the syringe labeled with a "1," then at the next dose, using the syringe labeled with a "2."

Please return all used and unused syringes and empty boxes to the clinic on your next visit. Used syringes should be placed in the special sharps container provided. All unused syringes should be returned in the original box.

If an injection is missed or something occurs where the full dose cannot be injected, contact your study center immediately for further instructions. Please record any missed doses on your subject dosing diary.

Remember to complete your dosing diary after each injection and to call the doctor's office if you are having problems administering your study medication.

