Crohn's Disease Activity Index (CDAI) CDAI components "Number of liquid or very soft stools" and "Abdominal pain" (Stool [liquid/soft] Frequency + Abdominal Pain Score; SFPS)	X	X ⁿ	X	X	X	X	X	X	X	X	X	X	X	X	X	X	X		
SES-CD Score	X								X								X		
Inflammatory Bowel disease Questionnaire (IBDQ)		X	X	X		X		X		X			X				X		
European Quality of Life 5 dimensions (EQ-5D)		X	X	X		X		X		X			X				X		
Work Productivity and Impairment Questionnaire (WPAI)		X	X	X		X		X		X			X				X		
Abdominal Pain Rating Scale		X	X	X	X	X	X	X	X	X			X				X		
Corticosteroid Taper ^d				X	X	X	X	X	X	X	X								
Monitor Adverse Events ^e		X	X	X	X	X	X	X	X	X	X	X	X	X	X	X	X	X	X
Study Drug Dispensing/Administration ^g		X	X	X	X	X	X	X	X	X	X	X	X	X	X	X	X	X	X

Table 1. Study Activities (Continued)

Activity	Screening Period (30 Days) ^a	12-Week Double-Blind Induction Study						44-Week Double-Blind Maintenance Study								Unscheduled Visit ^b	70-Day Follow-Up ^c									
		Baseline	Week 2	Week 4	Week 6	Week 8	Week 12 (Re-Randomization)	Week 14	Week 20	Week 26	Week 28	Week 34	Week 40	Week 42	Week 48			Week 56/Premature Discontinuation								
Dispense Subject Diary	X		X	X	X	X		X	X	X	X	X	X	X	X	X										
Subject Diary Review		X	X	X	X	X		X	X	X	X	X	X	X	X	X	X									X
Intestinal Biopsies ^d	X																									X

- a. The Screening period will be a minimum of 7 days for CDAI calculation. The CDAI calculated at Screening will serve as the Baseline CDAI. Baseline visit date will serve as the reference for all subsequent visits. A ± 3-day window is permitted around all study visits.
- b. Update inclusion/exclusion, prior and concomitant therapy, and medical/surgical history information to assure subject eligibility.
- c. Height will be measured at Screening only (with shoes off, and then adding 1 inch or 2.5 cm).

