9.0 Study Drug Exposure and Compliance

Study drug exposure and compliance will be summarized using the mean, standard deviation, minimum, median, and maximum. Exposure to study drug (total patient years) will be summarized by treatment group.

The number of injections received at each schedule time point will be summarized with number and percent for each treatment group.

Study Drug Exposure (in Days) during the induction period:

For subjects who discontinued from the Induction Study:

- Date of last dose of Induction Study drug – Date of first dose of Induction Study drug + 14 days

For subjects who completed the Induction Study:

- Date of first dose of Maintenance Study drug or date of first dose study drug in Study M14-347 – Date of first dose of Induction Study drug + 1 day,
Or
- Date of last dose of Induction Study drug + 14 – Date of first dose of Induction Study drug + 1 day, whichever is shorter.

The date of last dose of Induction Study drug is defined as the date of last study drug injection before the date of re-randomization into Maintenance Study. The date of first dose of Maintenance Study drug is defined as the date of first study drug injection on or after the date of re-randomization into Maintenance Study.

Study Drug Compliance:

Treatment compliance will be summarized for each treatment group in the ITT population. The treatment compliance is defined as the number of injections actually

taken by the subject divided by the number of injections planned to be taken by the subject during the induction period.

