10.3 Secondary Efficacy Analyses

For the analysis purpose, the secondary efficacy endpoints for the Induction Study are divided into two groups: (1) ranked secondary endpoints and (2) additional, non-ranked endpoints.

Ranked Secondary endpoints:

1. Proportion of subjects with sustained clinical remission (CDAI < 150) at both Weeks 4 and 12.

2. Proportion of subjects with CDAI < 150 at Week 4 and decrease in SES-CD > 50% from Baseline (or for a Baseline SES-CD of 4, at least a 2 point reduction from Baseline) at Week 12.
3. Proportion of subjects with clinical remission (CDAI < 150) at Week 12.
4. Proportion of subjects who discontinued corticosteroid use and achieved clinical remission (CDAI < 150) at Week 12 among subjects taking corticosteroids at Baseline.
5. Proportion of subjects with endoscopic remission (SES-CD \leq 4 and at least a 2 point reduction versus baseline and no subscore greater than 1 in any individual variable) at Week 12.
6. Change from Baseline in fecal calprotectin level at Week 4.
7. Proportion of subjects with hs-CRP < 5 mg/L and fecal calprotectin < 250 μ g/g at Week 4.
8. Proportion of subjects with CDAI < 150, hs-CRP < 5 mg/L, and fecal calprotectin < 250 μ g/g at Week 4.
9. Proportion of subjects with CDAI < 150, hs-CRP < 5 mg/L, SES-CD \leq 4 and at least a 2 point reduction versus baseline and no subscore greater than 1 in any individual variable, and fecal calprotectin < 250 μ g/g at Week 12.
10. Proportion of subjects who achieve an SES-CED \leq 2 at Week 12.
11. Proportion of subjects with clinical response (decrease in CDAI \geq 70 points from Baseline) at Week 4.
12. Proportion of subjects with clinical response (decrease in CDAI \geq 70 points from Baseline) at Week 12.
13. Proportion of subjects achieving response in IBDQ Bowel Symptom domain (increase of IBDQ bowel symptom domain score \geq 8) at Week 4.
14. Proportion of subjects achieving response in IBDQ Bowel Symptom domain (increase of IBDQ bowel symptom domain score \geq 8) at Week 12.

15. Proportion of subjects achieving response in IBDQ fatigue item (increase of IBDQ fatigue item score ≥ 1) at Week 12.

For these endpoints which are categorical variables, NRI method of imputation will be used for the missing values. LOCF will be used as a sensitivity analysis wherever applicable.

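### The Week 12 fecal calprotectin window closes at the first maintenance dose, without the 7 days allowed for SES-CD, so stool collected on a later day drops out of ranked endpoint 9

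*SAP*

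**What the plan says.** **The calprotectin window.** Induction SAP Section 6.0, Table 6 sets Week 12 at Rx Day 58 to 112 around nominal Day 85. Footnote b closes it at "Rx Day 112, or first dose of maintenance, or first dose of study drug in Study M14-347, whichever earlier". Section 9.0 fixes the first maintenance dose as the one "defined as the date of first study drug injection on or after the date of re-randomization into Maintenance Study". Under Protocol Section 5.1, CA subjects "will receive 40 mg adalimumab every other week beginning at Week 12". The subject instructions in Protocol Appendix G place the Week 12 injection at the site: "At Weeks 4, 6, 8, 12, 14, 20, 26, 28, 34, 40, 42 and 48 you will receive 1 injection at the clinic".

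**Stool collection.** Protocol Section 5.3.1.1, Fecal Calprotectin, allows collection at home: "If subjects are unable to provide a sample at the site visit, subjects will be sent home with a stool sample supply kit". It also requires collection before bowel preparation and return within 3 days of collection.

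**The SES-CD window.** Table 5 footnote b closes at "Rx Day 168, or first dose of maintenance + 7 days" (with the same allowance for Study M14-347), and denies the extra week to fistulas and EIM. Section 12.2 explains that the extension keeps collected endoscopies from being ignored.

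**Scoring.** Ranked endpoint 9 (Section 10.3) combines CDAI, hs-CRP, endoscopic remission and calprotectin below 250 µg/g at Week 12. The missing-data rule is "For these endpoints which are categorical variables, NRI method of imputation will be used for the missing values".

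**Other conventions.** Section 6.0 says that windowing throws away no post-baseline measurement on the CRF. It also counts evaluations made on the day of the first maintenance dose as induction data. Maintenance SAP Table 4 assigns calprotectin from maintenance Rx Day 2 to 148 to Week 26.

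**The concern.** Two components of one composite follow different cut-offs. After the same maintenance dose, an endoscopy up to 7 days later still counts as Week 12, while a stool sample taken the next day does not. Section 12.2 shows that the sponsor expected some Week 12 endoscopies to fall after the dose. Stool linked to such an endoscopy is due before its bowel preparation, so it may be collected after the dose with nobody departing from the stool instructions. Discarding it from Week 12 also conflicts with the SAP's own no-discard statement.

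At stake is a true success on endpoint 9 recorded as a failure. Endpoint 9 sits in a fixed testing sequence (Section 10.4), so missing significance there ends formal testing of endpoints 10 to 15. For the non-ranked change in calprotectin at Week 12, LOCF would carry the Week 4 value.

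**Working it through.** **1. The plan's own figures.** The documents give no rate or power for endpoint 9. To check the method, I reproduced the co-primary power by exact enumeration of Fisher's test (300 versus 200, two-sided 0.05). It is 99.4% for 50% versus 30% and 99.8% for 66% versus 44%. Under independence the joint power is 0.994 × 0.998 ≈ 99.2%. These agree with the stated 99%, about 99% and above 98%.

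**2. Window dates.** Inputs: Table 6 (58, 85, 112), Table 5 (+7 days) and the visit tolerance "A ± 3-day window is permitted around all study visits".
- The nominal window is symmetric: 85 − 58 = 27 and 112 − 85 = 27 days.
- With the dose on Day 85, the last 112 − 85 = 27 days cannot be used. With the dose on Day 82 or Day 88 it is 112 − 82 = 30 or 112 − 88 = 24 days.
- For the Day 85 subject, SES-CD stays open to 85 + 7 = Day 92.
- A Day 86 stool sample is maintenance Rx Day 86 − 85 + 1 = 2, inside the Week 26 window. It is used there unless another sample lies nearer Day 99.

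**3. Which samples are affected** (windowed by collection date)

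| Stool collected | Endoscopy | Calprotectin at Week 12 | SES-CD at Week 12 |
|---|---|---|---|
| On or before dosing day, whenever returned | Before dose | Kept | Kept |
| After dosing day, before bowel preparation | Within 7 days after dose | Outside | Kept |
| After dosing day, after bowel preparation | Before dose | Outside | Kept |

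The second row is the clear defect. In the third row the sample already departs from the collection instruction.

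**4. When the result changes.** Three conditions must hold together: the sample is collected on a day after the dose; no other sample lies from Rx Day 58 to the dose; and the subject truly meets all four components of endpoint 9.

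**5. Size.** Let f be the share of would-be responders lost, equal in both arms. The observed rate is p(1 − f), so the observed difference is (1 − f) times the true one. Neither f nor the endpoint 9 rates are in the documents, so all values below are assumptions (Fisher's exact, 300 versus 200).

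| True rates | Result | f = 0 | 5% | 10% | 20% |
|---|---|---|---|---|---|
| 25% vs 15% | Difference (points) | 10.0 | 9.5 | 9.0 | 8.0 |
| | Power | 77% | 74% | 71% | 64% |
| 15% vs 8% | Difference (points) | 7.0 | 6.65 | 6.3 | 5.6 |
| | Power | 64% | 61% | 58% | 52% |

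In the first scenario there are 300 × 0.25 + 200 × 0.15 = 105 true responders, so f = 5% means about 5 misclassified subjects.

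**The case against.** A reader might infer that every take-home Week 12 sample is lost. The documents do not support that. Stool is due before bowel preparation, and the site-read Week 12 SES-CD is a stratification factor for re-randomization (Protocol Section 8.3). The planned order is therefore stool, preparation, endoscopy, re-randomization, dose. A sample taken in that order is in the window, as is one taken on the dosing day, and late return of the kit does not matter. This argument stands and confines the loss mainly to the second row of the table.

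Other objections carry some weight:
- **The cut may be deliberate.** Tables 2, 3 and 4 close at the same dose, and SES-CD is the only stated exception. But CDAI rests on diary days before the visit, and blood is drawn before study drug at the visit (Protocol Section 5.3.1.1). Of the endpoint 9 components, only stool and endoscopy naturally fall on another day.
- **The date is ambiguous.** The formula under Table 6 uses the date of visit, while the Rx Day definition uses the event date. If a kit sample carries the visit date, it stays in the window. The SAP should say which applies.
- **The sample is not deleted altogether.** It may reappear as Week 26. That is true, but a stool sample from a few days after Week 12 represents Week 26 poorly.
- **The impact is limited.** Only one of 15 ranked endpoints uses Week 12 calprotectin, equal loss in both arms is conservative, and the planned observed-case analysis for endoscopy-related endpoints could expose such losses. This stands and bounds the importance of the point.

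**Conclusion.** The inconsistency is real and narrow. A stool sample collected on a day after the first maintenance dose is outside Week 12, while an endoscopy up to 7 days after the same dose is inside. Where that was the subject's only late-induction sample, a true success on endpoint 9 is scored as a failure. The effect is a modest attenuation of one ranked endpoint. The co-primary endpoints do not use calprotectin and are unaffected.

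This rests on windowing by collection date. The count of affected subjects cannot be derived from the documents; given the planned order of procedures, it is probably small. The power figures are illustrations under assumed rates and assumed equal loss, and do not estimate what will happen in this trial. It is a cheap improvement worth making before the induction data are unblinded.

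**What to change.** In Induction SAP Table 6 footnote b, keep Rx Day 112 as the outer limit and add 7 days to both dose-based limits (first maintenance dose and first Study M14-347 dose), whichever comes earliest, as Table 5 does for SES-CD. State that stool is windowed by collection date and that a sample on or before the dose is preferred if one exists. For a subject dosed on Day 85, usable samples then run to Day 92 (maintenance Rx Day 8).

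In Maintenance SAP Table 4, exclude from Week 26 any sample already used as Week 12.

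The cost is two SAP edits. A few samples will come from up to 7 days after a maintenance injection, which the SAP already accepts for the co-primary SES-CD; TDM adjustment first occurs at Week 14. The Week 12 value could then differ from the Maintenance Baseline value, which stops at maintenance Day 1; a sentence should say so. Samples taken after bowel preparation would also be admitted and should be flagged.
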